A power calculation was performed in nQuery Advisor (version 7.0) with the following assumptions: a type I error of 5%; a type II error of 7%; the titanium mesh group has a mean (SD) height gain of 5.2 (0.79) mm (Artzi 2003)¹⁵; the e-PTFE group has a mean (SD) height gain of 3.15 (1.12) mm (Simion 2007)⁶. The minimum sample size necessary was determined to be 7 subjects. To account for potential dropout, the study population will be increased to include 10 subjects. Up to 15 subjects will be consented (and considered enrolled) into the study to achieve these goals.

Statistical Analysis:

Counts and percentages, will be reported for categorical data. Mean and standard deviations will be reported for continuous data.

1. For the Aim 1, the height gain will be measured in millimeters (mm) and considered to be continuous data. The paired t-test will be used to compare the height gain after the healing following vertical ridge augmentation between the d-PTFE membrane group and the Ti-mesh group.

2. For the Aim 2, the mean incidence of post-operative complication in each group will be measured in percentage as categorical data. The Mann-Whitney U test will be used to compare the incidence of post-operative complications occurred in vertical ridge augmentation procedures between the d-PTFE membrane group and the Ti-mesh group.

3. For the Aim 3, the new bone formation will be measured in percentage as categorical data. The paired t-test will be used to compare the percentage of

new bone formation after the healing following vertical ridge augmentation between the d-PTFE membrane group and the Ti-mesh group.

All analyses will be performed using Stata (version 13.1)

Randomization:

Randomization will be performed in a 1:1 ratio using a balanced design based on a computer-generated randomization scheme, both for the location of the procedure, but also for the performed technique. Randomization will occur during visit 2.

Blinding:

The subjects will be blinded for the randomization assignment (Single-blinded). We will blind subjects by not informing them of their treatment allocation (d-PTFE membrane or Ti-mesh). If subjects do not see the preparation of the materials (d-PTFE or Ti-mesh), they will not be able to tell which procedure they receive. The preparation of d-PTFE membrane and Ti-mesh will be performed and delivered to the surgical site out of sight of participants during surgery.

C) Products

Group	Product 1	Product 2

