The pre-operative height of the bony crest will be evaluated on the pre-existing radiographs from the referring clinic if they are less than 6 months old. If recent radiographs do not exist, radiographs will be taken at this visit. Regardless of the subject's involvement in the study, it is standard of care to have radiographs taken within the past 6 months prior to surgery.

Visit 2: Surgery

Medical history will be reviewed as standard of care.

Eligibility and subject withdrawal criteria will be reviewed to ensure the subject still qualifies for the study.

Surgeries will be performed by either of two investigators.

The use of d-PTFE for vertical ridge augmentation will be randomly assigned to one side of the mouth of each subject (randomization is for research purposes) and Ti-mesh to the other side of mouth, and therefore, subjects will receive both of the following procedures:

*Guided Bone regeneration (GBR) procedure using a d-PTFE: (standard of care excluding clinical measurements)

The following steps will be performed following standard of care procedures: local anesthesia, muco-periosteal incision, full thickness flap reflection, de-cortication of the alveolar ridge, bone harvesting using bone scrapers, tenting screw placement, clinical measurements, DBBM graft material placement, the placement and stabilization of the d-PTFE membrane according to manufacturer's instructions, sutures.

* Guided Bone regeneration (GBR) procedure using Ti-mesh: (standard of care excluding clinical measurements)

The following steps will be performed following standard of care procedures: local anesthesia, muco-periosteal incision, full thickness flap reflection, de-cortication of the alveolar ridge, bone harvesting using bone scrapers, tenting screw placement, clinical measurements, DBBM graft material placement, the placement and stabilization of the titanium mesh according to manufacturer's instructions, sutures.

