Bone harvesting using bone scrapers will be performed during GBR procedures with both techniques (d-PTFE and Ti-mesh). Bone harvesting using bone scrapers is for harvesting particulate autogenous bone graft material. We will use a mixture of 50:50 DBBM and autogenous bone graft material for all vertical augmentation procedures in the study. Particulate autogenous bone graft will be harvested from the retromolar region of the mandible. This area is just next to the area of GBR procedures (posterior mandible) and will be visible after flap elevation for vertical augmentation. Therefore, we do not need any additional steps except harvesting autogenous bone graft. Intraoral harvesting by bone scrapers from the retromolar region is a simple and safe method for collecting cortical bone chips.

The intrasurgical clinical measurements of the ridge height will be taken during surgery. The distance between the top of the tenting screw and bone crest will be measured with a periodontal probe during the procedure.

Duration of each procedure and surgical complications including flap tear and bleeding will be collected. All outcome measurements will be performed by a Co-I who did not perform the surgery.

The subject will be asked to complete a pain/discomfort survey using VAS scale from zero to ten. A medication log will be given to the patient to track the number of pills of the prescribed painkiller they have taken in order to examine the amount of pain after the surgical procedures. The mean number of pills used after surgical procedures will be analyzed.

Post-operative medication will be prescribed following TUSDM standard of care guidelines.

Visit 3 (7±3 days after procedure): Post-operative Follow-up

Medical history will be reviewed as standard of care. Eligibility and subject withdrawal criteria will be reviewed to ensure the subject still qualifies for the study.

Each subject will have a post-operative visit, which is standard practice at TUSDM periodontology clinic. Standard of care procedures including suture removal and evaluation of surgical site will be performed.

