Radiographs will be taken. It is standard of care to have radiographs taken prior to implant placement. The post-operative (after the vertical GBR augmentation procedure) height of the bony crest will be evaluated on the radiographs taken as part of standard of care.

Visit 6 (Up to 1 month after Visit 5): Bone core harvesting, implant placement visit

Medical history will be reviewed as standard of care. Eligibility and subject withdrawal criteria will be reviewed to ensure the subject still qualifies for the study.

The subject will present for their regularly scheduled implant placement. The following steps will be performed following standard of care procedures: local anesthesia, muco-periosteal incision, full thickness flap reflection, membrane (Ti-mesh/d-PTFE) removal, clinical measurements, tenting screws removal, bone core harvesting, implant osteotomy, implant placement, and sutures.

The intrasurgical clinical measurements of the ridge height will be taken at during implant placement surgery. The distance between the top of the tenting screw and bone crest will be measured with a periodontal probe during the procedure. The bone height gain will be calculated by subtracting the second measurement from the first measurement (taken during initial surgery).

At the time of the implant placement a bone core will be harvested from each site of the implant locations for histological analysis. For the bone samples in this study, a hollow (trephine) bur, rather than solid bur, will be used to allow for sampling. A trephine bur with 3-4 mm diameter will be used. The core size will not exceed the amount of bone removal required for designated implants. Removal of bone is standard during implant placement in order to create space for the fixture.

The bone core biopsies will be placed in fixative and labeled with subject ID. The collected bone samples will be placed in alcohol for storage and stored in a basic science laboratory DHS-635.

The implant placement will not be considered a part of this study.

After Visit 6 - Laboratory analysis of bone core sample

Histological slides will be prepared and histomorphometric analysis will be performed by the commercial laboratory. The samples will be coded as subject numbers and histological analysis will be blinded. All collected bone core samples will be shipped to the laboratory by PI or Co-I.

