If after going through the consent form, the participant indicates s/he would like to discuss the study with associates or think about participating, then the meeting will be ended and the participant will be asked to contact the study when s/he makes her decision. If the participant contacts the study in the future for participation, s/he will be invited back to the clinic, and if informed consent is given at that time, study activities will begin then.

If the participant indicates s/he may be interested in participating after going through the consent form with the investigator, and the investigator determines the participant has the capacity to provide informed consent, the participant will be asked to provide informed consent at that time. Patients will certify their willingness to participate in the study by signing

and dating the IRB approved informed consent document. The subject will be given a copy of the consent form.

If any new finding requires any change to the informed consent form, the subject will be reconsented.

Non-English speaking subjects will not be enrolled in the study because study staff at this time are not certified, prepared, or trained to translate or communicate in any language other than English. The study budget does not allow for the payment of translation services at this time.

3) Study Location
TUSDM

4) Personnel
The PI will be responsible for ongoing communication with the IRB.

PI or [name] will perform all surgical procedures including bone biopsy. The Co-I will perform clinical measurements, surveys and follow-up visits.

PI or Co-I will be responsible for obtaining informed consent. The consent process will be begun by PI, medical Co-I, or a research coordinator. If a research coordinator begins the consent process, PI or medical Co-I will complete it.

PI or medical Co-I will be available to answer any medical questions. PI, Co-I, or a research coordinator will be responsible for maintaining records.

The research coordinating team at TUSDM have worked on numerous clinical studies and have a history of performing the consent process with subjects and assessing competency. They are CITI education certified and GCP trained. In addition, they have attended multiple trainings related to these tasks.

5) Payment for Participation
(a) Compensation

Subject will not be charged a fee of \$738 for each bone augmentation surgery.

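### Only subjects are blinded: nothing in the plan masks the Co-I who probes height gain, although the order of surgical steps would largely allow it

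*Combined protocol and SAP*

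**What the plan says.** The Blinding paragraph in III.B reads "The subjects will be blinded for the randomization assignment (Single-blinded". The rest of it explains only how subjects are kept unaware of the material used.

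The Rationale names clinical height gain as the primary goal. III.E defines it as the distance from the top of the tenting screw to the bone crest, read with a periodontal probe at Visit 2 and again at Visit 6, the second reading being subtracted from the first.

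On who reads, III.E (Visit 2) says "All outcome measurements will be performed by a Co-I who did not perform the surgery". III.G.4 (Personnel) gives surgery to the PI or one other operator and adds "The Co-I will perform clinical measurements, surveys and follow-up visits". III.E also says "Surgeries will be performed by either of two investigators".

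The follow-up text under Visit 4 lists exposure of the membrane or mesh among the complications to be assessed. The laboratory section after Visit 6 makes the histological analysis blinded. No comparable statement covers the height reading.

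**The concern.** Reading a probe by hand involves judgement, and Aim 1 declares in advance that Ti-mesh is expected to gain more height. A reader who knows which side had the mesh can lean, without intending to, towards that expectation. In a split-mouth comparison a lean that differs by technique adds to the mean paired difference. It does not average out over subjects, and the paired t-test cannot tell it from a true effect. The trial is small (7 subjects required, 10 planned), and the plan takes the trouble to mask a later aim, histology, while leaving its primary endpoint without the same protection.

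**Working it through.** 1. *Visit 2 step order.* d-PTFE side: "tenting screw placement, clinical measurements, DBBM graft material placement, the placement and stabilization of the d-PTFE membrane". Ti-mesh side: "tenting screw placement, clinical measurements, DBBM graft material placement, the placement and stabilization of the titanium mesh". On both sides the reading falls after the screw and before graft and barrier, so no barrier is in the field. Randomization takes place during Visit 2 (III.B), but its order relative to this reading is not given.

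2. *Visit 6 step order.* "membrane (Ti-mesh/d-PTFE) removal, clinical measurements, tenting screws removal, bone core harvesting". The reading falls after the barrier is off and while the screws are still in. Again no barrier is in the field.

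3. *Where the reader could still learn the technique.*
   - At Visit 2, if allocation is already open or the reader stays while barriers are placed. Procedure duration and surgical complications are collected then, and the next sentence assigns all outcome measurements to the Co-I.
   - At follow-up, when a barrier is exposed.
   - From the Visit 5 radiographs, which are taken before the barriers come out at Visit 6.
   - At Visit 6, if the reader watches the barrier being removed.

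   The plan closes none of these routes. Each can be closed, or at least narrowed, by sequencing or by dividing duties.

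4. *The plan's own figure.* Inputs from III.B: Ti-mesh 5.2 (SD 0.79) mm, e-PTFE 3.15 (SD 1.12) mm, type I error 5%, type II error 7%, n = 7. Sidedness is not stated; two-sided is assumed.
   - Planned difference: 5.2 − 3.15 = 2.05 mm.
   - Root-mean-square SD: √((0.79² + 1.12²)/2) = 0.969 mm.
   - Two-sample t-test (noncentral t): power 0.909 at 6 per group and 0.952 at 7, so 7 is the smallest n reaching 0.93.
   - Paired t-test at n = 7: power 0.906 with within-subject correlation r = 0, and 0.930 with r = 0.1. The documents give no r.

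   The stated 7 is reproduced, and masking the reader does not change it.

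5. *Illustrative size.* Let b be the net lean in the mean paired difference (Ti-mesh minus d-PTFE), whichever reading it comes from. The values of b are assumptions.
   - 0.25/2.05 = 12%
   - 0.5/2.05 = 24%
   - 1.0/2.05 = 49%

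6. *Sensitivity of the test.* Suppose there is no true difference and the mean paired difference is b alone. The SD of the difference is √(0.79² + 1.12² − 2r × 0.79 × 1.12), which is 1.371 mm at r = 0 and 0.997 mm at r = 0.5. The noncentrality is b√n/SD on n − 1 degrees of freedom. Chance that the two-sided 5% paired t-test is significant:

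| Assumed b | n = 7, r = 0 | n = 7, r = 0.5 | n = 10, r = 0 | n = 10, r = 0.5 |
|---|---|---|---|---|
| 0.25 mm | 7% | 9% | 8% | 11% |
| 0.5 mm | 13% | 20% | 18% | 30% |
| 1.0 mm | 37% | 60% | 54% | 81% |

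Both b and r are assumed, so the table shows how the test responds to a lean. It does not predict that one will occur.

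**The case against.** The plan already has safeguards. The reader is not the operator, the measurement runs between two fixed landmarks, and the baseline reading precedes the barrier and may precede allocation. These stand and lower the likely bias. None of them hides the technique at Visit 6.

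Three stronger readings are tempting, and the documents do not support them.

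- *That the reader is known to be unmasked.* No section says the Co-I knows the technique. That is an inference from the single-blind statement and from silence. What can be said is that nothing in the plan prevents it. Nor does the plan say that one fixed reader probes both sides at one sitting.

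- *That masking needs no extra staff.* Two operators and a Co-I are mentioned, so it is plausible, but it is not shown. The obvious swap, with the non-operating surgeon as reader, has its own problems. That person would sometimes be the PI, who evaluates subjects with adverse events (III.F) and so may learn of an exposed barrier. The plan also does not say that the same surgeon operates at Visits 2 and 6.

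- *That the result would be materially wrong.* Neither the probe's graduation nor any reading error is given. If readings are to the nearest millimetre, a steady 0.5 mm lean on one side is already the limit of rounding, and 1.0 mm would need full opposite leans on the two sides. Even then 2.05 − 1.0 = 1.05 mm of the planned difference would remain.

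It is also fair to say that masking at Visit 6 may be imperfect, since fixation marks or tissue appearance could reveal the technique. That limits the benefit but does not remove it.

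**Conclusion.** The point holds as a gap in the protection of the primary endpoint. Blinding covers subjects only. The height reader is independent of the operator but not masked by anything in the plan, and the same role attends the visits where the technique can become visible. Both readings are scheduled at moments when no barrier is in the field, so most of the gap can be closed by sequencing.

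No size can be derived from the documents. The 12%, 24% and 49% figures, and the error rates in the table, rest wholly on assumed leans of 0.25, 0.5 and 1.0 mm and, for the error rates, on assumed correlations of 0 and 0.5. The change should be made because it is cheap and the direction of expectation is stated. The documents do not show that bias has occurred, and the point does not by itself invalidate the design or the sample size.

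**What to change.** Amend III.B (Blinding), III.E (Visits 2 to 6) and III.G.4 to say:

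- The height-gain reader is masked to side allocation.
- At Visit 2 each reading is taken before allocation is opened to the reader, who is absent while barriers are placed. Someone else records procedure duration and surgical complications during that time.
- At Visit 6 the reader enters for each side only after that side's barrier has been removed and is out of sight. This works whether the two sides are operated in parallel or in sequence.
- The allocation record and the Visit 5 radiographs are withheld from the reader.
- Where existing investigators allow, a different team member who did not operate on that subject does that subject's Visit 3-5 assessments. Where this is not possible, the report should say so.
- The same reader is used at both visits within a subject.

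The cost is protocol wording and some scheduling. Two downsides remain: between-reader variation if readers differ across subjects, and possibly incomplete masking at Visit 6. The treatment, the analysis and the sample size do not change.

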Comparing the Efficacy and Morbidity of Two Vertical Ridge Augmentation Techniques

NCT number: 02703480

Document Date: 12/1/2020

I) Introduction

The aim of the randomized prospective controlled clinical trial, a split mouth design, is to compare the efficacy and morbidity of the two vertical ridge augmentation techniques: Titanium mesh (Ti-mesh) technique and Guided Bone Regeneration (GBR) technique using a high-density polytetrafluoroethylene (d-PTFE) membrane. The efficacy will be measured by the height gain (Aim 1) and the bone core histology/histomorphometry (Aim 3). The morbidity will be assessed by the incidence of post-operative complications (Aim 2).

Aim 1: Compare the height gain obtained in vertical ridge augmentation procedures using intrasurgical clinical measurement in millimeter.

We hypothesize that the height gain obtained after the six months healing period following vertical augmentation using Ti-mesh will be more, compared with that of a d-PTFE membrane.

Aim 2: Identify and compare the rate of post-operative complications following vertical ridge augmentation procedures using a complication case report form (CRF).

We hypothesize the incidence of surgical complications occurring in vertical ridge augmentation procedures with Ti-mesh will be less frequent, compared with a d-PTFE membrane.

Aim 3: Evaluate and compare bone core histology by quantifying new bone formation using histomorphometric analysis.

We hypothesize that the new bone formation using vertical ridge augmentation procedures with a Ti-mesh membrane will be greater, compared with d-PTFE membrane.

II) Background and Rationale

Background:

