The present study presents various complications that are possible with the vertical ridge augmentation procedures, both with a d-PTFE and titanium mesh. The common complications that can occur are: exposure of d-PTFE membrane or titanium mesh, infection, paresthesia, postoperative pain, swelling and bleeding. However, there is no additional risk participating in the study compared to the standard of care of vertical ridge augmentation. d-PTFE membrane cannot be used under load bearing conditions, which is not related to the study procedure.

As with surgeries involving metallic implants there is a chance for foreign body sensitivity. Where material sensitivity is suspected appropriate tests should be made to rule out this possibility prior to implantation.

Risk of bone core biopsy

In the bone core biopsy, a trephine will be used and a bone core sample of the hard tissue will be collected and finalized with standard bur prior to implant placement. No more than the standard amount of bone will be removed for this study. There is no additional risk related to this procedure. The risk associated with bone biopsy is over-drilling of bone (create a bigger hole than the size of hole that is necessary for bone core) when harvesting a bone piece. However, the risks associated with bone biopsy are minimal because a bone core drill is smaller than a standard implant drill, which is necessary to place an implant.

2) Benefits

There is no medical benefit to the subject for participating in this study.

3) Alternatives

Study subjects will be informed that they have the right to withdraw from the study at any time for any reason, without prejudice to their dental care. The alternative is not to participate in the study. Patients may receive the standard care for vertical augmentation procedures from postgraduate students of the TUSDM periodontology clinic at standard clinic fees.

E) Study Procedures

Visit 1: Screening

Informed consent will be obtained by the principal investigator or a co-investigator. The subjects will be instructed to read the informed consent form (ICF), given ample time to have any questions answered, and then instructed to sign the ICF. Subject will be given a copy of the ICF.

Subject will be asked to complete demographic information and a medical history.

Inclusion/exclusion criteria will be evaluated.

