For research, information regarding bleeding, presence of infection, bruising, and/or other complications will be collected. Each subject will complete a survey to evaluate the level of pain/discomfort, bleeding, and swelling following the surgical procedure for each side – each classified on a VAS scale from zero to ten. In addition, the subject will return his or her completed medication log.

Visit 4 (21±3 days after procedure): Post-operative Follow-up

Medical history will be reviewed as standard of care. Eligibility and subject withdrawal criteria will be reviewed to ensure the subject still qualifies for the study.

Each subject will have a post-operative visit, which is standard practice at TUSDM periodontology clinic. Standard of care procedures including suture removal and evaluation of surgical site will be performed.

For research, information regarding bleeding, presence of infection, bruising, and/or other complications will be collected. Each subject will complete a survey to evaluate the level of pain/discomfort, bleeding, and swelling following the surgical procedure for each side – each classified on a VAS scale from zero to ten.

Follow-up visits during the six month post-operative period of the vertical ridge augmentation surgery will be scheduled. Standard of care procedures and evaluations will be completed during follow-up visits. The surgical sites will be evaluated after the vertical ridge augmentation procedures, in order to assess the presence of postoperative complications, such as the exposure of a d-PTFE membrane or Ti-mesh, infection, swelling, paresthesia or any other complications. All will be noted in the subject's axiUm record and reviewed at the time of Visit 4.

Visit 5 (6±1 months after Visit 4): Evaluation visit

Medical history will be reviewed as standard of care. Eligibility and subject withdrawal criteria will be reviewed to ensure the subject still qualifies for the study.

Surgical sites will be evaluated and the subject's axiUm record will be reviewed for any complications.

Each subject will complete a survey to evaluate the level of pain/discomfort, bleeding, and swelling following the surgical procedure for each side – each classified on a VAS scale from zero to ten, as at Visit 3.

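### Aim 2 does not define what counts as a complication, so routine swelling, bleeding and bruising may dilute the comparison of the two techniques

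*Combined protocol and SAP*

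**What the plan says.** Section I sets Aim 2 as a comparison of post-operative complication rates recorded on a complication case report form, which the document does not reproduce. The hypothesis is that complications with Ti-mesh "will be less frequent, compared with a d-PTFE membrane". No rate or difference is given.

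Section III.B, Statistical Analysis, item 2, reduces this to one summary: "the mean incidence of post-operative complication in each group will be measured in percentage as categorical data". The groups are compared with a Mann-Whitney U test, although every subject receives both techniques, one per side.

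Section III.E says what is collected. At Visits 3 and 4, "information regarding bleeding, presence of infection, bruising, and/or other complications will be collected". Over the six-month follow-up, sites are checked for events "such as the exposure of a d-PTFE membrane or Ti-mesh, infection, swelling, paresthesia or any other complications". At Visits 3 to 5 each subject also completes a survey "to evaluate the level of pain/discomfort, bleeding, and swelling following the surgical procedure for each side", each item on a 0 to 10 VAS.

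The Risk section (section III.D, Assessment) lists the events that may happen: "The common complications that can occur are: exposure of d-PTFE membrane or titanium mesh, infection, paresthesia, postoperative pain, swelling and bleeding". Table 1 schedules complication evaluation at Visits 3, 4 and 5. Barriers are removed at Visit 6.

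**The concern.** The collected events are of two kinds. Barrier exposure, infection and paresthesia bear on how the technique performed. Swelling, bleeding and bruising can follow the flap surgery itself, and by section III.E both sides get the same incision, flap reflection, decortication, bone harvest and tenting screws. Only the barrier differs.

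The plan sets no severity threshold, does not close the list, and does not say whether the incidence means any event per side, a count per side, or a rate for each type. Under the any-event reading, a side with ordinary bruising is the same kind of case as a side with an exposed mesh, and a real difference in exposure or infection is pulled towards zero. Because both sides are operated on the same day, symptoms may also occur on both sides of a subject together. Such pairs are concordant and carry no information for a paired comparison. Morbidity is the stated secondary goal and is meant to inform treatment choice, so which events count should not be settled after the data are seen.

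**Working it through.** **Inputs from the plan.** 10 planned subjects, hence 10 pairs of sides; type I error 5%, taken here as two-sided. The plan has no Aim 2 figure to reproduce: its sample size (7, raised to 10) is for height gain, and no complication or symptom rate appears anywhere.

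**Assumed inputs.** Rate h of exposure, infection or paresthesia: 40% on one technique and 10% on the other. Rate q of a routine symptom among sides without such an event, equal for both techniques: varied from 0 to 90%.

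**Step 1: dilution under an any-event rule.** Composite rate = h + (1 − h)q = 1 − (1 − h)(1 − q). The difference between techniques is therefore (h1 − h2)(1 − q).

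- q = 50%: 1 − 0.6 × 0.5 = 70% and 1 − 0.9 × 0.5 = 55%
- q = 80%: 1 − 0.6 × 0.2 = 88% and 1 − 0.9 × 0.2 = 82%
- q = 90%: 1 − 0.6 × 0.1 = 94% and 1 − 0.9 × 0.1 = 91%

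**Step 2: discordant pairs expected in 10.** With independent sides and composite rates a and b, this is 10 × [a(1 − b) + b(1 − a)]. With q = 0: 10 × (0.4 × 0.9 + 0.1 × 0.6) = 4.2. If a symptom instead occurs on both sides of a subject or on neither, it is 4.2 × (1 − q).

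| q | Composite rates | Difference | Discordant pairs, independent sides | Discordant pairs, shared symptoms | Exact McNemar power, independent sides |
|---|---|---|---|---|---|
| 0 | 40% v 10% | 30 points | 4.2 | 4.2 | 7.6% |
| 50% | 70% v 55% | 15 points | 4.8 | 2.1 | 2.3% |
| 80% | 88% v 82% | 6 points | 2.57 | 0.84 | 0.1% |
| 90% | 94% v 91% | 3 points | 1.39 | 0.42 | below 0.01% |

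At q = 50% with independent sides the number of discordant pairs does not fall. Power falls because symptoms add discordance in both directions: the expected split goes from 3.6 against 0.6 to 3.15 against 1.65.

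**Step 3: what 10 pairs can show.** For m discordant pairs all in one direction, the two-sided exact p-value is 2 × 0.5^m: 0.0625 for m = 5 and 0.031 for m = 6. At least six discordant pairs are needed. With six to eight, all must point the same way (7 against 1 gives 2 × 9/256 = 0.070); with nine or ten, one may go the other way (8 against 1 gives 2 × 10/512 = 0.039).

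**Step 4: power once routine symptoms are excluded.** Exact McNemar, 10 pairs, independent sides: 2% for 30% v 10%, 8% for 40% v 10%, 19% for 50% v 10%, 49% for 60% v 5%. For 40% v 10%, the Mann-Whitney test on 0/1 data (large-sample form, no continuity correction) has about 29%, but it treats the two sides as separate people.

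**The case against.** A reader might infer that Aim 2 does count pain, swelling and bleeding, so that nearly every operated side becomes a case. The documents do not support this. The list that includes pain is risk text, and pain is called a complication nowhere else. The case report form is not shown. The complication items for Visits 3 and 4 name bleeding and bruising but not swelling; swelling enters with the six-month follow-up, as one example among several. No symptom rate is given.

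A reader might also infer that these symptoms are counted twice. They are recorded in two places, but nothing puts the VAS scores into the Aim 2 incidence.

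Nor is an any-event rule the only reading. A mean incidence tested by Mann-Whitney U fits a count per side equally well, and a count has no 100% ceiling. It would still give a bruise the same weight as an exposed mesh. Rates for each type would avoid the problem, but the plan does not specify them.

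The strongest objection is that 10 pairs are too few for a test in any case: a narrow definition gives only about 8% power for 40% v 10%. That stands. It would be wrong to blame the symptoms alone for a failure to separate the techniques. It does not excuse the missing definition, because with so few pairs the clear rates by component are the main usable result.

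**Conclusion.** The concern holds in conditional form. Aim 2 has one summary incidence and no case definition, and its collection text mixes routine symptoms with technique-related events. If any such event makes a side a case, the difference between techniques shrinks by the factor (1 − q): an assumed 30 points become 15, 6 or 3 at q = 50%, 80% or 90%. The factor assumes that q is the same for both techniques; all rates are assumptions. Halving at q = 50% shows that the point does not need near-universal symptoms. Whether saturation would occur cannot be told from the documents. This should be put right before analysis. It affects a secondary aim and leaves the height-gain comparison untouched.

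**What to change.** - Make the main Aim 2 outcome, for each side, yes/no for barrier exposure, infection or paresthesia.
- Fix the window to match the scheduled evaluations, for example from surgery to Visit 5. If events found at barrier removal are to count, add a complication evaluation at Visit 6 to Table 1.
- Tabulate each component separately, and the remaining complications in their own table. Bruising belongs there, since it has no VAS item.
- Analyse pain, swelling and bleeding as within-subject differences in the per-side VAS scores already collected at Visits 3 to 5.
- Replace the Mann-Whitney U test with a paired exact (McNemar) analysis, and present the paired difference with its confidence interval.
- State that Aim 2 is estimation and that absence of a significant difference is not evidence of similar morbidity.

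**Cost.** A change of wording in the Aim 2 endpoint and analysis text, with no new data unless Visit 6 is added. The headline rate no longer includes expected symptoms. Power stays low after the change (about 8% for 40% v 10%), and the exact paired test has less nominal power than the unpaired one under the independence assumption; that is the price of an analysis that respects the split-mouth design.
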